**Intervention Group (Pharmacist Interventions):**

Participants enrolled in the intervention group will receive pharmacist interventions, in addition to standard care outlined in the Alberta College of Pharmacist Standards of Practice for Pharmacist and Pharmacy technicians (9).

Unique pharmacist interventions will include the following (in person) at enrolment (month 0) and at the scheduled month 1, 3, and 6 in-person or telehealth pharmacist meetings:

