**1) Patient Assessment:**

- Recording participant scores from the combined PHQ-9/GAD-7 questionnaire tool (Appendix 4) completed by the participant, which includes:
  - PHQ-9 (Patient Health Questionnaire 9-item), a multipurpose instrument for screening, diagnosing, monitoring and measuring the severity of depression
  - GAD-7 (Generalised Anxiety Disorder 7-item)
- If determined clinically relevant by the pharmacist partner will assess:
  - appearance, current mood, sleeping patterns, mental health, medical history, social history, family history, relationships with others, suicidal ideation, previous suicide attempts or hospitalizations, current employment status.

2) Pharmacist-initiated prescribing dose adjustment, medication change to different medication, deprescribing, or prescribing adjunctive add-on medication, to achieve clinical response and/or remission of MDD and/or GAD and establish appropriate cognitive/functional status as per CAMAT guidelines (7, 8).

3) Provide regular communication updates with the patient's family physician after each contact with the patient (via fax or electronic charting).

4) Providing medication counselling and educational support to the participant.

5) Identification of adverse drug effects, drug interactions, or severe deterioration (i.e. suicide attempt)

6) Interim telephone/telehealth follow-up conducted by the pharmacist partner since the last in-person follow-up & a minimum of 1-2 weeks after the last in-person follow-up that involved a dose adjustment, prescribing of adjunctive medication, or discontinuation of therapy. (Note: a telephone follow-up does not replace the scheduled in-person/telehealth follow-up).

7) Collaborate with physician to arrange referral to psychologist, psychiatrist, counsellor or social worker for psychotherapy

Should the participant from the interventional group drop out or complete the 6 month study period, they will be offered to continue with similar interventional care or standard pharmacist care but no data will be collected since their dropout or following study completion.

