**Control Group (Standard Pharmacist Care):**

Patients randomised to the standard pharmacist care groups will receive:

- Standard pharmacist care, as outlined in the Alberta College of Pharmacist Standards of Practice for Pharmacist and Pharmacy technicians (9), and physician care with no specific interventions for the duration of the 6 month study period.
- Should participants from the usual care group drop out or the participant completes the 6 month study period, they will be offered care similar to the interventional group or standard pharmacist care but no data will be collected since their dropout or following study completion.

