### **Secondary outcomes:**

- Difference in the clinical improvement rates (proportions of participants achieving clinically significant treatment response) between the pharmacist intervention and standard pharmacist care groups from baseline until the end of the study period, using the PHQ-9 and GAD-7 score.
  - For our study, clinically significant treatment response for the PHQ-9 is defined as a reduction in PHQ-9 score by at least 50% from baseline; adequate treatment response for the GAD-7 is defined as a drop in the GAD-7 score by at least 50% from baseline.
- Difference in the proportion of participants with MDD to achieve PHQ-9 score <5 (i.e. remission/no depression) between the pharmacist intervention and standard pharmacist care groups
- Difference in the proportion of participants with GAD to achieve GAD-7 score <5 (i.e. remission/no anxiety) between the pharmacist intervention and standard pharmacist care groups
- Percentage difference in self-reported safety concerns disclosed by participant to pharmacist partner anytime during the study period, between the pharmacist intervention and standard pharmacist care groups:
  - Adverse medication effects (e.g. dizziness, GI intolerance, bleeding, palpitations suggestive of prolonged QTc interval, etc.)

- Suicidal ideation, attempt at suicide
  - Causing withdrawal from study
- 

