### **Sample size and analytical plan:**

#### Sample Size Calculation:

Lindell et al (2018), who evaluated the impact of a psychiatric clinical pharmacists intervention on the change in PHQ-9 and/or GAD questionnaire scores (14), reported a baseline PHQ-9 mean of 15.2 (Standard deviation [SD] of 6.9) and GAD mean of 12.0 (Standard deviation [SD] of 5.8).

Using those reported values and the following assumptions of an 80% power and a 2 sided alpha of 0.05, a sample size of:

- 84 patients (42 in each group) is required to detect a 4.3 point difference in the mean reduction in PHQ-9 scores between the intervention and control group
- 80 patients (40 in each group) are required to detect a 8.3 point difference in the mean reduction in GAD scores between the intervention and control group.

We selected the larger sample size of 84 patients and inflated it by 10%(47 in each group) to account for potential losses to follow-up and withdrawal of consent.

A Data Safety monitoring board will be formed to review adverse events, and data will be sent once recruitment reaches 25% (24 participant) recruitment.

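### The between-arm safety comparison is confounded by unequal ascertainment: events count only if disclosed to the pharmacist, and the intervention arm has more scheduled contacts that look for them

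*Protocol*

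**What the plan says.** Protocol, Secondary outcomes, defines the safety endpoint as "Percentage difference in self-reported safety concerns disclosed by participant to pharmacist partner anytime during the study period", compared between the two arms. It covers adverse medication effects, suicidal ideation or attempt, and concerns that lead to withdrawal.

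Protocol, Intervention Group, delivers the pharmacist's work "at enrolment (month 0) and at the scheduled month 1, 3, and 6 in-person or telehealth pharmacist meetings". The numbered list that follows includes "Identification of adverse drug effects, drug interactions, or severe deterioration", an assessment of suicidal ideation where the pharmacist finds it relevant, and interim telephone or telehealth follow-up after treatment changes. These calls are extra: "a telephone follow-up does not replace the scheduled in-person/telehealth follow-up".

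Protocol, Control Group, gives standard pharmacist care and "physician care with no specific interventions for the duration of the 6 month study period". Under Both Groups, the only study procedures common to the arms after enrolment are the PHQ-9/GAD-7 and the month-6 visit before which it is completed. No adverse-event question is mentioned there. Recording interventions describes logging of interactions and interventions performed, not a common safety form. The Analytical Plan assigns secondary outcomes to ANCOVA, t-test or chi-square and does not address unequal ascertainment.

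**The concern.** An event enters this endpoint only through a conversation with the pharmacist, and the number and purpose of those conversations are part of the randomised treatment. Looking for harm is a component of the intervention, and what it finds becomes the safety outcome. Allocation thus affects the count by two routes: through any real effect on harm, and through the chance that a harm is noticed.

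The error can go both ways. Pharmacist prescribing could appear to raise adverse effects or suicidal ideation when it does not. Or a real excess could be put down to closer follow-up, because the data cannot tell the two apart. A real reduction in harm could also be masked. The protocol says its results are meant to inform regulators, government and patients about prescribing pharmacists, so a safety contrast that cannot be interpreted is a material loss even though it is a secondary outcome.

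**Working it through.** **Plan's own figure.** The protocol states no figure for the safety outcome. The only one used here is the arm size. For a 4.3-point PHQ-9 difference with SD 6.9, two-sided alpha 0.05 and 80% power, the t-based calculation gives 41.4, so 42 per group. Then 42/0.9 = 46.7, so 47 per group. Both match the protocol.

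**Scheduled contacts after baseline.** Participants are starting medication, so the enrolment contact can hardly reveal effects of that treatment and is left out.

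| | Intervention | Control |
|---|---|---|
| Scheduled contacts | months 1, 3, 6 = 3 | month 6 = at most 1 |
| Interim calls after treatment changes | yes, additional | none stated |
| Stated task of identifying harms | yes | none stated |
| Routine standard-care contact | yes | yes |

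**Illustration.** Let p be the true risk (equal in both arms), s the probability of spontaneous disclosure (including at routine contacts), q the detection probability per scheduled contact, and k the number of such contacts. Then

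observed risk = p × [1 − (1 − s)(1 − q)^k].

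The values of p, s and q are assumptions; none is in the protocol.

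Worked case, p = 0.40, s = 0.10, q = 0.50:
- Intervention, k = 3: 0.40 × [1 − 0.90 × 0.125] = 0.40 × 0.8875 = 35.5%
- Control, k = 1: 0.40 × [1 − 0.90 × 0.50] = 0.40 × 0.55 = 22.0%
- Difference 13.5 points; ratio 0.8875/0.55 = 1.61. With 47 per arm, the chance of p < 0.05 is about 30% although true harm is equal.

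The true risk cancels from the ratio, so over p = 20% to 60% the ratio depends only on q:

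| q | k = 3 | k = 1 | Spurious ratio |
|---|---|---|---|
| 0.30 | 0.691 | 0.370 | 1.87 |
| 0.50 | 0.8875 | 0.550 | 1.61 |
| 0.70 | 0.976 | 0.730 | 1.34 |

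One interim call (k = 4 versus 1) moves the range to 1.36–2.12.

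**A true benefit.** If the intervention truly lowers the risk to 0.67 of control, the observed ratio is 0.67 × 1.87 = 1.25, 0.67 × 1.61 = 1.08 or 0.67 × 1.34 = 0.90. The benefit is shrunk or reversed.

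**More routine disclosure.** With s = 0.50 and q = 0.50 the factors are 1 − 0.50 × 0.125 = 0.9375 and 1 − 0.50 × 0.50 = 0.75, a ratio of 1.25. The bias is smaller but in the same direction.

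**The case against.** The strongest defence is that ascertainment in controls is unknown rather than limited to one contact. They receive pharmacist care under the cited practice standards. Appendix 5 lists, as information potentially gathered in that care, suicide attempts in the past year and a medication history that looks for possible harms. Disclosure counts at any time, including at ordinary pharmacy visits. This stands as a limit on size. It does not remove the problem, because the intervention is given on top of standard care: routine contacts occur in both arms and the scheduled excess remains.

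Second, the month-6 visit may include a safety enquiry on a form not shown. That would give the 3 versus 1 comparison used above, not equality. Nor can a later analysis plan recover events that nobody asked about.

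Third, PHQ-9 item 9 is collected in both arms at months 0 and 6. That is true, but the endpoint is not defined by it, and it does not cover adverse effects or attempts.

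Fourth, unequal contact is inherent in testing enhanced follow-up, and the primary outcome is not touched. Both statements are fair. They limit the importance of the point, but unequal contact does not require the safety endpoint to be measured through it.

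Two stronger readings are tempting and unsupported. A reader might infer that the difference measures contact frequency and not harm. In fact it mixes the two, and withdrawals in particular depend less on how often the pharmacist calls. A reader might also infer that the monitoring board will judge the arms on these same counts. The protocol says only "A Data Safety monitoring board will be formed to review adverse events"; it does not say that the board receives this outcome or compares arms on it.

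**Conclusion.** The point holds as a confounded comparison. Under the plan as written, the arms differ by design in how safety events are found, and the observed difference cannot be separated into harm and detection. The expected direction is more events in the intervention arm when true harm is equal.

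The size cannot be fixed from the protocol. Under the stated assumptions (3 versus 1 contacts, 10% spontaneous disclosure, detection of 30% to 70% per contact) the spurious risk ratio is 1.34 to 1.87, with 35.5% against 22.0% in the worked case. The model assumes that contacts detect independently and that spontaneous disclosure is equal in both arms. Effects that persist and are reported at month 6 in either arm, or fuller routine disclosure, would narrow the gap; interim calls would widen it. The point concerns one secondary outcome, and it is worth correcting because the correction is cheap.

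**What to change.** 1. Add a short fixed checklist on adverse effects, suicidal ideation and suicide attempt, covering the period since enrolment, to the month-6 questionnaire already sent to both arms. Base the between-arm safety comparison on these answers.
2. Use PHQ-9 item 9 at month 6 as a supporting measure of current ideation only.
3. Keep withdrawals due to safety concerns as a separate count in both arms.
4. Report pharmacist-disclosed events descriptively by arm, with the number of contacts, and without a between-arm test.

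The cost is a few items on an existing electronic form and a short change to Secondary outcomes. Clinical care is unchanged.

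The drawbacks should be stated in the protocol. Recall over six months is imperfect, though it applies to both arms. Item 9 asks only about the last 2 weeks, so it misses ideation in between. Participants who drop out before month 6 are missed, since no data are collected after dropout; the separate withdrawal count covers only part of that gap. Finally, the Randomization section lets participants without electronic access complete the questionnaire with the pharmacist, so collection will not be fully identical; the mode of completion should be recorded.

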**Exclusion criteria:**

- Pregnancy
  - Non-Alberta residents
  - Unwilling or unable to participate in regular follow-up visits
  - Unwilling to participate/sign consent form
  - $\geq 2$  suicide attempts per year
  - Severe, psychotic, and catatonic depression
  - Current substance abuse, intoxication, addiction, or withdrawal requiring acute care management
  - Patients diagnosed with comorbid anxiety disorders other than GAD, including: panic disorder, agoraphobia, specific phobia, social anxiety disorder, obsessive-compulsive disorder, posttraumatic stress disorder
  - Patients diagnosed with comorbid depressive disorder other than MDD, including: depressive disorder due to another medical condition (e.g. hypothyroidism, MS, OSA, Parkinsons, stroke, TBI, Vitamin B12 insufficiency, Huntington disease, adrenal insufficiency, mononucleosis, systemic lupus erythematosus), adjustment disorder with depressed mood
  - Patients diagnosed with concurrent ADHD, bipolar disorder, schizophrenia and schizoaffective disorder
- 

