**Recruitment:**

Potential participants will be identified and approached by the pharmacist partners (pharmacists with APA and PraCID) if they are picking up or dropping off their prescription for a medication listed in Appendix 1 and 2.

Medication indication will be verified with the patient for the treatment of diagnosed MDD and/or GAD (and if additional verification is required--collateral from physician, Netcare consult note, or pharmacy record).

As part of the standard of pharmacist practice (as outlined in the Alberta College of Pharmacist Standards of Practice for Pharmacist and Pharmacy technicians [9]), a patient is clinically assessed for pharmacotherapy appropriateness by the pharmacist partner. This process is performed by the pharmacist partner and is the initial screen to determine if the patient meets any inclusion or exclusion criteria.

Determined by the pharmacist partner, if a patient meets the inclusion criteria for the study and does not meet any exclusion criteria, the patient will be asked if he/she wants to participate in the study and be provided with a formal invite letter to review.

If the patient agrees on participating, he/she will be asked to sign a written informed consent form. After signing the consent form, the patient will be enrolled in the study and randomised as a study participant using the secured electronic study website/database (developed by EPICORE and secured at the University of Alberta research office).

The participant's physician will receive the notification letter for physicians, from the pharmacist partner, to inform him/her that the participant has agreed to participate in the study. Should the physician refuse to have the participant participate in the study, the participant will not be enrolled into the study.

Should the participant decline recruitment into the study, they will continue to receive the same level of pharmacist care as outlined in the Alberta college of pharmacists standards of practice (9).

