### **Randomization**

Multiple pharmacies are involved in participant enrollment--therefore, once informed written consent is obtained from the patient, the patients will be randomised by stratified randomization using a blocking factor to assign participants to either intervention or usual care groups.

Each participant will be assigned a unique identifier number and group allocation for the duration of their participation in the study--this unique identifier and allocation will also be communicated to and recorded by the pharmacy partner in the participant's patient profile to ensure consistency of the degree of pharmacist interventions described by the group the participant is allocated to.

The participant will be sent a secured electronic link (to the contact number or email they provided in the written consent form) that will include the participant's unique identifier and group allocation and the electronic version of the PHQ-9/GAD-7 questionnaire tool to complete and submit electronically. If the participant is unable to provide a means for the electronic link to be sent, the questionnaire tool can be completed with the pharmacist partner in person prior to their scheduled in-person/telehealth pharmacist meetings.

The study data (i.e. the participant's submitted electronic questionnaire tool results) will be sent directly to a centralised and secured website/database to ensure allocation concealment for the investigational team.

The participant questionnaire scores are available to the pharmacist partner via a secured electronic website/database prior to their scheduled in-person/telehealth meeting with the pharmacist partner.

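### Suicidal ideation is compared as disclosed at any time, but the intervention arm has more scheduled chances to disclose it, so an excess there need not mean harm

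*Protocol*

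**What the plan says.** The Protocol's Secondary outcomes section compares between arms the "Percentage difference in self-reported safety concerns disclosed by participant to pharmacist partner anytime during the study period". One listed component is "Suicidal ideation, attempt at suicide". Neither line refers to the participant's status at entry.

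Four other parts of the protocol bear on how this outcome behaves.

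- **Eligibility.** The Exclusion criteria rule out two or more suicide attempts per year and "Severe, psychotic, and catatonic depression". Ideation is not excluded.
- **Intervention arm contacts.** Pharmacist interventions take place "at enrolment (month 0) and at the scheduled month 1, 3, and 6 in-person or telehealth pharmacist meetings". They include "Recording participant scores from the combined PHQ-9/GAD-7 questionnaire tool (Appendix 4) completed by the participant", and item 9 of that tool asks about thoughts of death or self-harm. Topics to assess include "suicidal ideation, previous suicide attempts or hospitalizations", but only where the pharmacist judges them relevant. Interim telephone or telehealth follow-up is added, for example after a dose change.
- **Control arm contacts.** Controls receive standard pharmacist and physician care without study-specific interventions. The Both Groups section sets the shared questionnaire at months 0 and 6.
- **What the pharmacist sees.** The Randomization section says "The participant questionnaire scores are available to the pharmacist partner via a secured electronic website/database". The outcome does not say whether an item 9 answer seen in this way is a disclosure.

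**The concern.** Pharmacists in the intervention arm may change, stop or add psychotropic drugs, so new or worsening suicidality is the most serious harm the intervention could cause. The comparison meant to detect it counts what participants tell the pharmacist, and the two arms do not have the same scheduled occasions for telling. With no true effect, ideation that is present and persistent has more chances to be recorded in the intervention arm. A reader of the final percentages could not separate new harm from illness present at entry that came up more often. Month 0 item 9 is collected in both arms and would make that separation possible, but the outcome does not use it.

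**Working it through.** **Plan figures.** The protocol states no rate or power for this outcome. The group sizes used below are its own: 42 per group (4.3 points, SD 6.9, 80% power, two-sided 5%) and 47 after inflation. The normal formula gives 2 × (1.960 + 0.842)² × 6.9² / 4.3² = 40.4, rounded up to 41. The t-test version gives 41.4, rounded up to 42. Then 42 / 0.90 = 46.7, rounded up to 47. Both figures reproduce.

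**Assumed inputs (not in the protocol).** Share with ideation at entry b = 10% to 40%; chance of disclosure per asking d = 0.1 to 1; askings equal and independent.

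**Step 1. Month 0 item 9 counts as a disclosure, and disclosure is complete and equal.** The share ever counted is b + (1 − b)e, where e is new ideation among those free of it at entry. Take e = 5% control and 15% intervention, a relative risk of 3.0 in that subgroup.

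| b | Control | Intervention | Difference | Relative risk | Power, 47 per arm |
|---|---|---|---|---|---|
| 10% | 14.5% | 23.5% | 9 points | 1.62 | 20% |
| 30% | 33.5% | 40.5% | 7 points | 1.21 | 11% |
| 40% | 43.0% | 49.0% | 6 points | 1.14 | 9% |

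The difference equals (1 − b) × 10 points, which is exactly the difference in new ideation among all randomised. Entry ideation dilutes the relative effect and power but creates no false difference.

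**Step 2. Item 9 does not count; only what is told to the pharmacist does.** Suppose no true effect, ideation lasting from entry to month 6, and four askings against two. The disclosure gap is [1 − (1 − d)⁴] − [1 − (1 − d)²] = (1 − d)² − (1 − d)⁴. Writing x = (1 − d)², this is x − x², which peaks at x = 0.5 (d = 0.293) with value 0.25. So 50% against 75% is the ceiling. The false excess is b times the gap:

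| d | Gap (points) | b = 10% | b = 20% | b = 40% |
|---|---|---|---|---|
| 0.1 | 15.4 | 1.5 | 3.1 | 6.2 |
| 0.3 | 25.0 | 2.5 | 5.0 | 10.0 |
| 0.5 | 18.8 | 1.9 | 3.8 | 7.5 |
| 0.7 | 8.2 | 0.8 | 1.6 | 3.3 |
| 0.9 | 1.0 | 0.1 | 0.2 | 0.4 |
| 1.0 | 0 | 0 | 0 | 0 |

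The range is 0 to 10 points. Adding 5% new ideation in both arms, disclosed in the same way, a nominal 5% two-sided pooled test with 47 per arm rejects as follows for b = 10% to 40%: 9% to 22% at the ceiling, 7% to 13% at d = 0.5, 5.3% to 6.4% at d = 0.7, and 5.0% at d = 0.9.

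Duration matters. At d = 0.3 the gap is 0 if entry ideation ends at month 0, 21 points if it lasts to month 1, and 36 if it lasts to month 3 but not to 6 (three askings against one). A three-against-one count at d = 0.5 and b = 40% gives 15 points. These are special cases outside the four-against-two model.

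**Step 3. Unequal contact also affects new ideation.** Let new ideation of 5% to 10% in both arms start evenly over six months and persist. With d = 0.3 to 0.7, asking at months 1, 3 and 6 against month 6 alone gives a false excess of about 0.6 to 1.5 points. For example, at 10% and d = 0.5: 0.10 × [(1/6)(0.875) + (1/3)(0.75) + (1/2)(0.5)] = 6.5% against 0.10 × 0.5 = 5.0%. A reference to entry status alone therefore does not remove the problem.

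**Step 4. Item 9 at months 0 and 6 only.** Scheduled askings are two in each arm, so the schedule itself adds no difference. With 42 per arm observed, the 95% CI half-width is 1.96 × √(2p(1 − p)/42): 9.3 points at p = 5% and 12.8 at p = 10%.

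**The case against.** - **This belongs in the analysis plan.** An event definition and a baseline rule are commonly left to that document, which is not at hand, and their absence is not the point here. What the protocol does fix is the source and window of the count and the unequal schedule, and those together produce the problem.
- **Asking about ideation is not mandated more often.** A reader might infer that the intervention arm is questioned directly about ideation at every meeting. The documents do not support that: direct inquiry is at the pharmacist's discretion, and the only scheduled question is item 9. If item 9 counts, entry ideation is caught equally at month 0. If it does not, the number of direct askings is unstated in both arms, and four against two is only a stand-in. This limits the claim to unequal opportunity.
- **Entry capture may already be similar.** Before consent, "a patient is clinically assessed for pharmacotherapy appropriateness by the pharmacist partner", whichever arm follows. Appendix 5 lists past-year suicide attempts among information gathered in standard care, and the Both Groups section mentions an in-person month 6 visit. These narrow the gap by an unknown amount, though the pre-consent assessment precedes the study period.
- **List layout.** In the extracted text the line about withdrawal from the study sits beneath the suicidality line. If it qualifies that line, unchanged ideation would rarely count. This may be an extraction artefact and cannot be settled here.
- **Redefining the event could do worse.** A reader might conclude that the outcome must become new or worsened ideation as judged by the pharmacist. With no true effect (5% new, 10% worsening, both disclosed 50% against 75%) and entry ideation captured equally, the present rule gives a false difference of 1.1, 0.9 and 0.75 points at b = 10%, 30% and 40%; the redefined rule gives 1.4, 1.6 and 1.8. If entry ideation is also disclosed 50% against 75%, the order reverses: 3.6, 8.4 and 10.8 against 1.4, 1.6 and 1.8. If the unblinded pharmacist mislabels 10% of disclosed unchanged ideation as worse in the intervention arm only, the redefined rule rises to 2.1, 3.7 and 4.5. That is a trade-off, so redefinition is optional.

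**Conclusion.** The point stands in a limited form. The disclosed-ideation comparison is unequally ascertained by design, and ideation at entry is eligible, so an intervention-arm excess could not be read as harm without further information. The size cannot be derived from the protocol. If month 0 item 9 answers count as disclosures, entry ideation produces no false difference and only dilutes the relative effect. If they do not, persistent entry ideation could produce a false excess of 0 to about 10 points, assuming 10% to 40% with ideation at entry and four against two equal askings.

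A reader might take 10 points, or a 22% chance of a false significant result, as the expected size. The documents do not support that: those figures sit at the model's ceiling with 40% entry ideation, and the excess is under half a point at 90% disclosure per asking. Nor do they show that bias must occur. This is one component of a secondary outcome, a Data Safety monitoring board reviews adverse events, and power is low under any rule.

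**What to change.** Keep the disclosed-event comparison and add a comparison of PHQ-9 item 9 on the schedule both arms share.

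1. Give a month 0 by month 6 shift table of item 9 by arm, with the between-arm difference and 95% CI for emergent ideation (0 to 1 or more) and for worsening (any increase).
2. Use observed month 6 answers and show missing answers by arm. Do not apply the Analytical Plan's last-observation rule here: it would carry a month 1 or 3 answer forward in the intervention arm but only a month 0 answer in controls.
3. Leave the intervention arm's month 1 and 3 answers out of this comparison.
4. List disclosed ideation by arm according to month 0 item 9 status, and state in the interpretation that disclosed events are unequally ascertained.

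The cost is some protocol wording, one table and one listing, all from data already collected; no visits or questionnaires are added. The limits should be stated. Item 9 covers only two weeks, so ideation arising and resolving between months 0 and 6 is missed. The questionnaire link shows the group allocation, so even month 0 answers are not blind. With a half-width of about 9 to 13 points, the result is descriptive.
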